In summary, while these studies have demonstrated the potential role of BoNT for ET there remains limitations that have yet to be addressed. It is unclear if the perceived efficacy of BoNT in tremor reduction is diminished by associated extensor weakness. It is also unclear if BoNT injection of flexors alone is equally efficacious as the injection of both flexor and extensor muscles. If injecting extensor muscles is essential, can the ratio between extensor and flexor muscles be adjusted to give efficacy with no weakness? Furthermore, although previous studies have demonstrated significant objective improvement in tremor severity, they did not observe significant improvements in quality of life (QOL), functional improvement, and global improvement.

With these limitations in mind, we propose a pilot, single center, double blind, randomized, parallel, placebo controlled trial comparing 2 BoNT injection patterns for treatment of moderate to severe essential tremor. To minimize the potential for extensor weakness, we will inject the extensor muscles with 1/3 the dose used for the flexor muscles (a 3:1 ratio of BoNT injected for flexor to extensor as compared to the previous studies which used a 3:2 ratio). Our primary outcome and secondary outcomes as detailed below will include patient global impression scale as well as other functional and QOL scales.

6) STUDY OBJECTIVES:

Study aim:

To compare the efficacy of botulinum toxin (BoNT) injections in forearm flexors plus extensor muscles versus flexors alone for the treatment of essential hand tremor (ET).

Hypothesis:

We hypothesize that both patterns of BoNT injection (flexors plus extensors, flexors alone) will be equally efficacious in decreasing tremor, but that patients in the flexors alone group will experience less motor weakness and therefore report greater global improvement in symptoms.

We acknowledge the possibilities that patients in the flexors plus extensors group may perceive greater improvement in tremor severity due to the additional injection of the extensor compartment and that the injection of the extensor compartment may be well tolerated because the injected dose is only 1/3 of the dose for the flexor compartment.

Primary Outcome Measure:

Difference in 6 week post injection on a Patient Global Impression Scale-Improvement Subscale (PGI-I)

Secondary Outcome Measures:

1. *Improvement in 6 week post injection in tremor rating scale.*

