2. *Difference in the mean Quality of Life in Essential Tremor Questionnaire (QUEST) at Week 6 from baseline between wrist flexors versus wrist flexors plus extensors group.*
3. *Improvement in 6 week post injection in Clinician Global Impression Scale-Improvement Subscale (CGI-I).*
4. *Difference in grip strength post injection between the two groups at 6 weeks*
5. *12 week post injection patient global improvement scale*

6. *12 week post injection tremor rating scale*
7. *Difference in the mean QUEST score at Week 12 from baseline between wrist flexors versus wrist flexors plus extensors group.*
8. *12 week post injection clinician global improvement scale*
9. *Difference in grip strength post injection between the two groups at 12 weeks.*

Tertiary Outcome Measures

1. *Monitor changes in depression using PHQ-9 at 6 weeks*
2. *Monitor changes in anxiety using GAD-7 at 6 weeks*
3. *Monitor changes in depression using PHQ-9 at 12 weeks*
4. *Monitor changes in anxiety using GAD-7 at 12 weeks*

The scales that will be used in the study are below:

Global assessment graded by patient and clinician (PGIS and CGIS respectively) on -4 to +4 scale

- -4 = severe worsening
- 0 = no change
- +4 = complete abolishment of symptoms

Tremor Rating scale (TRS) at rest, posture and kinetic

- 0 = none perceived
- 1 = slight (barely noticeable)
- 2 = moderate, noticeable, probably not disabling (<2cm excursions from affected part)
- 3 = marked, probably partially disabling (2-4cm excursions)
- 4 = severe, coarse, disabling (>4cm excursion)

Kinetic tremor will be measured using motor tasks including handwriting and pouring. Patients will be asked to write the sentence "Today is a nice day" with their dominant hand. They will also be asked to draw a spiral. Pouring will be assessed by asking the patient to pour water from one cup to another.

QUEST will also be administered at baseline and follow up visits to assess functional impairment of tremor in activities of daily living.

Grip strength will be assessed using dynamometer.

7) STUDY DESIGN/METHODS:

We propose a pilot, single center, double blind, randomized, parallel, placebo controlled trial comparing 2 BoNT injection patterns for treatment of moderate to severe essential tremor.

We will recruit 20 patients with ET. The following inclusion and exclusion criteria will be used during the screening visit.

Inclusion Criteria

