1. Age 18 and over, male or female patient with ET involving at least their dominant hand, as diagnosed by a movement disorders neurologist.
2. Having bothersome hand tremor in dominant hand with a hand TRS ≥ 2
3. On stable medications during last 30 days prior to enrollment.

Exclusion Criteria

1. Presence of secondary causes of tremor, such as dystonia and parkinsonism
2. Any contraindication to botulinum toxin injections (e.g. motor neuron disease, neuromuscular junction disease, etc.)
3. History of surgical treatment for ET.
4. Dementia as defined by DSM-V criteria
5. Patients with suboptimally treated depression and significant depressive symptoms as defined by a PHQ-9 score of ≥ 15 (PHQ-9 scores 1-4 Minimal depression; 5-9 Mild depression; 10-14 Moderate depression; 15-19 Moderately severe depression; 20-27 Severe depression). Antidepressant medications, prescribed for depression or anxiety, will be allowed if the patient has been on a stable dose for at least 30 days.
6. Patients with suboptimally treated anxiety and significant anxiety symptoms as defined by a GAD-7 score of ≥ 15 (GAD-7 scores 0-4: minimal anxiety; 5-9: mild anxiety; 10-14: moderate anxiety; 15-21: severe anxiety). Anti-anxiety medications, prescribed for anxiety, will be allowed if the patient has been on a stable dose for at least 30 days.
7. Significant renal, hepatic, cardiac and thyroid disease

At the screening visit, if patient meets inclusion criteria and signs informed consent, patient will be randomized to one of two paradigms. Tremor will be rated based on Tremor Rating Scale (TRS) and Tremor Severity Scale (TSS). We will also obtain baseline evaluation of depression and anxiety, using PHQ-9 and GAD-7 respectively. In addition we will evaluate grip strength using dynamometer. Patients will be randomized to receive either injections of 150 units of abobotulinumtoxinA (Dysport[®]) in flexor compartment of dominant arm (75 units in flexor carpi radialis [FCR] and 75 units in flexor carpi ulnaris [FCU]) along with placebo in extensor carpi radialis (ECR) and extensor carpi ulnaris (ECU) or 75 units in FCR and FCU and 25 units in ECR and ECU. Injections will be done in dominant arm only. We will reduce dose in extensor by 66% of that given in flexor as opposed to previous RCTs where dose was reduced by 33% (Jankovic et al. 1996; Brin et al. 2001).

- Group 1 – plus Extensors: BoNT 200 units total (75U FCR, 75U FCU, 25U ECR, 25U ECU).

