- Group 2 – Flexors alone: BoNT 150 units total (75U FCR, 75U FCU, 0UECR, 0U ECU).

The patients will be seen in follow up at 6 weeks and again at 12 weeks. At these times we will repeat all baseline measures and in addition have patients evaluate treatment response using a patient global impact scale ranging from -4 (severely worse) to +4 (no more tremor) with 0 meaning no change. Clinicians will be asked to complete the same scale. Figure 2 depicts the outline of our study design.

Figure 2: Study Design

Visit	1	2	3
Type	Screening/Baseline (injection)	Post injection week	Post injection week
Time	0	6 weeks	12 weeks
Informed Consent	X		
History and PE	X	X	X
Concomitant Meds	X	X	X
Adverse Events		X	X
TRS	X	X	X
QUEST	X	X	X
PHQ-9	X	X	X
GAD-7	X	X	X
PGIS		X	X
CGIS		X	X
Grip Strength	X	X	X

Procedure/test:

The BoNT injections will take place in a dedicated clinical research space, located in the CNR Movement Disorders clinic in the U ("Mellen") building. No other patient will be present and the door will be closed to protect patient privacy. The patients will come in the morning when tremor will be evaluated clinically. Each patient will receive BoNT injections into dominant upper extremity using protocol outlined above. We will evaluate patients at week 6 and 12 post injection. At baseline visit, the nurse who is mixing the toxin will not be blinded to the treatment arm, but both the patient and PI who will be injecting as well as administering the rating scale will remain blind.

Randomization will be done using a computer program and each subject will be assigned an envelope which nurse will have access to and open when she is mixing the agent.

Statistical analysis:

Assessment of tremor improvement - We will compare average result of PGIS and CGIS at week 6 and week 12 between two groups. Furthermore we will compute percent change of TRS and QUEST for each follow-up visit as compared to the baseline. Given the small sample size, Mann-Whitney U test will be used for calculations.

Based on the previous studies (Jankovic et al. 1996; Brin et al. 2001), mean change in TRS and PGIS was 1 point (about 25% improvement on a 4-point scale) with a standard deviation of 0.7 points at week 6 post injection. To achieve an alpha of 0.05 and a power of 80%, we estimate a sample of size of 18 total patients with 9 in each treatment group. Accounting for an estimated 10% attrition rate we will recruit 20 total patients into this trial.

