APPENDIX

Scales

FLEXd-ET

Tremor Rating Scale

Subject ID _____

Visit number _____

Dominant Hand _____

Please use below grading for items 1-3

- 0 = none perceived
- 1 = slight (barely noticeable)
- 2 = moderate, noticeable, probably not disabling (<2cm excursions from affected part)
- 3 = marked, probably partially disabling (2-4cm excursions)
- 4 = severe, coarse, disabling (>4cm excursion)

1. At Rest _____
2. Posture (arms 90° perpendicular in front of patient) _____
3. Action/Intention (Finger to nose) _____
4. Handwriting (Please write *Today is a nice day in line below*) _____

0 = Normal

1 = Mildly abnormal

2 = Moderately abnormal. Legible, but with considerable tremor

3 = Marked abnormal. Illegible

4 = Severely abnormal. Unable to keep pencil or pen on paper without holding down with other hand

5. Spiral drawings (on back of sheet) _____

0 = normal

1 = Slightly tremulous. May cross lines occasionally

2 = Moderately tremulous or crosses line frequently

3 = Accomplishes task with great difficulty. Many errors

4 = Unable to complete drawing

6. Pouring _____

0 = normal

1 = more careful, but no water spilled

2 = spills a small amount of water (up to 10% of total amount)

3 = Spills a considerable amount (>10-50% of total amount)

4 = Unable to pour water without spilling most of the water

FLEXd-ET

Patient Global Impression Scale

Subject ID _____

Visit number _____

Dominant Hand _____

Please circle which number best corresponds to overall improvement in symptoms after injection

Severely worse

No Change

No further symptoms

-4 -3 -2 -1 0 +1 +2 +3 +4

FLEXd-ET

Clinician Global Impression Scale

Subject ID _____

Visit number _____

Dominant Hand _____

Please circle which number best corresponds to overall improvement in symptoms after injection

Severely worse

No Change

No further symptoms

-4 -3 -2 -1 0 +1 +2 +3 +4

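### Percent change in the TRS is planned without naming a score: by item it has no value at a zero baseline, and on a total it over-weights low baselines

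*Combined protocol and SAP*

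**What the plan says.** All references are to the combined protocol and SAP.

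- **Section 6, list of scales.** The TRS is introduced as "Tremor Rating scale (TRS) at rest, posture and kinetic", with one 0 to 4 grading. Writing, spiral drawing and pouring are then described as motor tasks. No composite is defined.
- **Section 6, secondary outcomes 1 and 6.** The TRS is an outcome at weeks 6 and 12. Neither entry names a score.
- **Section 7, Inclusion Criteria, item 2.** "Having bothersome hand tremor in dominant hand with a hand TRS ≥ 2".
- **Section 7, Statistical analysis.** The metric is given as: "Furthermore we will compute percent change of TRS and QUEST for each follow-up visit as compared to the baseline". The test is Mann-Whitney U. The sample size paragraph treats one point as "about 25% improvement on a 4-point scale".
- **Appendix, Tremor Rating Scale form.** There are six items: rest, posture, finger to nose, handwriting, spiral and pouring. The instruction "Please use below grading for items 1-3" covers the first three; the other three have their own 0 to 4 anchors. There is no total line.

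No section says whether the TRS means one item, the worst item, a mean or a sum, for any of these uses.

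**The concern.** Percent change needs a defined score and a non-zero baseline. The plan supplies neither for the TRS. The two obvious ways to fill the gap each give a poor outcome measure, for different reasons. A single item can start at 0, so a ratio to baseline may not exist. A total does not have that problem here, but a ratio to baseline makes a small change in a mildly affected patient look as large as a big change in a severely affected one.

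The TRS is the only listed outcome that grades observed tremor item by item, and it bears on the part of the hypothesis that expects both injection patterns to reduce tremor equally. With 9 evaluable patients per arm, a few missing or reordered values can shift the comparison. Leaving the score open also allows it to be chosen after the data are seen.

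**Working it through.** **Inputs**
- Six items, each 0 to 4 (Appendix form), so a six-item total runs from 0 to 6 × 4 = 24.
- Entry threshold of 2 (Inclusion Criteria, item 2).
- Percent change from baseline and Mann-Whitney U (Statistical analysis).
- 1-point difference, SD 0.7, alpha 0.05, power 80%, 9 per arm, 10% attrition, 20 recruited (Statistical analysis). Sidedness is not stated. I assume two-sided, because the section goes on to ask about superiority in either direction.

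**Step 1: the plan's own sample size.** By the normal approximation, n per arm = 2 × [SD × (z₀.₉₇₅ + z₀.₈₀) / difference]² = 2 × [0.7 × (1.960 + 0.842) / 1]² ≈ 7.69, so 8 per arm. The two-sample t-test (noncentral t) needs 9 per arm, with power 81.2%. Attrition: 18 / 0.90 = 20. The stated 18 and 20 reproduce.

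**Step 2: percent change by item.** Percent improvement = 100 × (baseline − follow-up) / baseline. At a baseline of 0 the denominator is 0, so 0 to 0 and 0 to 1 both have no value. If entry is met on one item graded 2 or more, the other five items can be 0. A sub-score of items 1 to 3 can also be 0, if entry is met on items 4 to 6. The plan gives no rule for these cases. Each patient lost in this way is 1/9, or 11%, of an arm in that item's comparison.

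**Step 3: percent change on the six-item total.** If entry means a sum of at least 2, or any item of at least 2, the lowest possible baseline total is 2. If it means a six-item mean of at least 2, the lowest is 6 × 2 = 12. Percent change of the total is therefore always defined under these readings. Its behaviour is shown below.

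| Baseline total | Follow-up total | Points gained | Percent improvement |
|---|---|---|---|
| 2 | 1 | 1 | 1/2 = 50% |
| 4 | 3 | 1 | 1/4 = 25% |
| 12 | 11 | 1 | 1/12 = 8.3% |
| 20 | 11 | 9 | 9/20 = 45% |

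**Step 4: effect on the planned test.** Mann-Whitney uses only the order of the values. It limits how far an extreme percentage can pull the result, but it keeps the ordering: row 1 (50%) ranks above row 4 (45%), although the second patient improved by nine times as many points.

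**The case against.** **The natural reading is a single 0 to 4 grade.** The threshold of 2 and the reference to a 4-point scale both fit one item. On that grading the first two steps are "1 = slight (barely noticeable") and "2 = moderate, noticeable, probably not disabling (<2cm excursions from affected part"), so a cut-off of 2 agrees with a trial described as "comparing 2 BoNT injection patterns for treatment of moderate to severe essential tremor". This largely stands for entry. It does not say which item, and it is the reading under which percent change on the remaining items can be undefined.

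**A reader might infer that barely noticeable tremor can qualify.** That needs a sum. Of the 2⁶ = 64 profiles with every item at 0 or 1, 64 − 1 − 6 = 57 have a total of at least 2. No section says the threshold is a sum, and the criterion also requires the tremor to be bothersome and the diagnosis to come from a movement disorders neurologist. Entry on rest tremor alone is likewise only an arithmetic possibility, in a trial that excludes parkinsonism. Nor do low-severity entry and undefined percent change occur together if one score is used throughout: a qualifying sum is at least 2, and a qualifying item is graded at least moderate. Both can occur only if entry uses a sum and the outcome uses items, which the documents neither state nor rule out.

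**Absolute change also depends on baseline.** A patient who starts at 2 cannot fall by more than 2. This is true. However, absolute change always exists, records worsening from 0, and gives each point the same weight.

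**This is a single-centre pilot of 20, and the TRS is secondary.** This stands, and it limits the importance of the point.

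**Conclusion.** The concern holds for the TRS percent-change metric. By item, the metric has no value at a zero baseline; on a total, it can rank a one-point fall above a nine-point fall. The documents give no distribution of baseline scores, so the number of patients affected cannot be estimated. The examples show what the metric permits, not how often it will happen.

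The reach is secondary outcomes 1 and 6. The primary outcome is the PGI-I, and the sample size arithmetic reproduces. A reader might infer that the study is underpowered because one point is 1/24 = 4.2% of a six-item total and not 25%. The documents do not support that: nothing says the assumed point applies to the total, and one point on each of six items is 6/24 = 25%.

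What remains on entry and powering is a need for reconciliation. Section 6, the inclusion criterion, the Statistical analysis section and the Appendix form should agree on which TRS score is meant.

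**What to change.** 1. For secondary outcomes 1 and 6, name one dominant-hand TRS total in advance, for example the sum of the form's items. Decide before unblinding whether the rest item is left out.
2. Add a total line to the Appendix form.
3. Compare absolute change from baseline between groups at weeks 6 and 12 with the planned Mann-Whitney test. Report percent change descriptively only.
4. Separately, state which TRS score the entry criterion and the sample size paragraph refer to, and bring the four places into line. Which items qualify a patient is for the investigators to decide.

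The cost is protocol and form wording, with no new assessments. The small downside is that results will be less directly comparable with reports that give percent improvement; the descriptive percentages partly offset this.

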Both RCTs, however, presented significant caveats. Although patients had significant improvement in tremor rating scales and objective assessments, none had a change in functional rating scales. Most BoNT injected patients in both studies had finger weakness. One RCT reported worse extensor weakness (50% moderate weakness, 42% mild weakness) as compared to flexor (Jankovic et al. 1996), while the other noted “finger drop” in the BoNT injected (Brin et al. 2001). Although claimed “unrelated” in one of the trials, it is possible that lack of subjective sense of improvement evidenced by functional rating scale was related to finger extension weakness. This argument is supported by an open-label study of BoNT injection (Pacchetti et al. 2000). This open-label study electrographically identified the most involved muscles using the surface electrodes placed on the skin overlying extensor carpi radialis (ECR), extensor carpi ulnaris (ECU), flexor carpi radialis (FCR), flexor carpi ulnaris (FCU), brachioradialis, pronator teres (PT), biceps, and triceps. Only muscles that showed significant tremor were injected with BoNT, hence wrist extensors were not injected in all patients (Pacchetti et al. 2000). Although dose and distribution of injected flexor muscles varied amongst patients, only 15% of the patients had finger extension weakness (Pacchetti et al. 2000). Furthermore, there was a significant improvement in both tremor severity and functional rating scales (Pacchetti et al. 2000). It is therefore possible that poor outcome on subjective functional rating scale in both RCTs were related to weakness. In addition, both RCTs had rigid treatment protocol implementing a fixed BoNT dose in predetermined muscles regardless of the disease severity. Lack of subjective improvement in some patients enrolled in these RCTs might be due to the mismatch between administered dose and severity of symptoms; for example, higher dose for mild tremor might exaggerate weakness, while low dose for moderate to high severity tremor might lead to under treatment.

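### Baseline tremor severity, already scored at visit 1, plays no part in the primary PGI-I comparison of about 10 patients per arm, so precision is left unused and the result is exposed to chance imbalance

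*Combined protocol and SAP*

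**What the plan says.** - **Allocation** (Section 7, Procedure/test): "Randomization will be done using a computer program and each subject will be assigned an envelope". The nurse opens the envelope when preparing the injection. No stratification, blocking or minimization is stated.
- **Primary outcome** (Section 6): PGI-I at week 6, rated from -4 to +4. The visit table (Figure 2) shows no baseline PGI rating, because the scale itself rates change.
- **Analysis** (Section 7, Statistical analysis): a two-group Mann-Whitney comparison with no covariate. Baseline enters only for TRS and QUEST, as percent change.
- **Severity range** (Section 7, Inclusion Criteria): "Having bothersome hand tremor in dominant hand with a hand TRS ≥ 2". The appendix TRS form has six items, each scored 0 to 4, and the protocol does not say which item or sum is the hand TRS.
- **Regimens** (Section 7): one fixed regimen per arm at every eligible severity, 200 units in total with extensors and 150 without. The flexor doses are the same in both arms.
- **Background** (Section 5), on the two earlier trials: "both RCTs had rigid treatment protocol implementing a fixed BoNT dose in predetermined muscles regardless of the disease severity", and "Lack of subjective improvement in some patients enrolled in these RCTs might be due to the mismatch between administered dose and severity of symptoms".

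**The concern.** The primary outcome is how much better the patient feels. Section 5 raises the possibility that this depends partly on how tremor severity matches the dose: "higher dose for mild tremor might exaggerate weakness, while low dose for moderate to high severity tremor might lead to under treatment". If severity does influence PGI-I, an arm that happens to receive more of the severe patients has its PGI-I shifted for reasons unrelated to the injection pattern. With about 10 patients per arm such splits are not rare, and an unadjusted comparison does nothing to correct the one that occurs. The variable needed to correct it is already measured before treatment.

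Two things are at stake. One is how far the single observed difference can be read as an effect of the extensor injection. The other is precision that would cost nothing to recover.

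**Working it through.** **1. The plan's own sample size.** Inputs from Section 7, Statistical analysis: difference 1 point, SD 0.7, alpha 0.05 (taken as two-sided, because the stated question runs in either direction), power 80%, attrition 10%. For a two-sample t-test with 9 per arm, the noncentrality is 1 / (0.7 × √(2/9)) = 1 / 0.330 = 3.03 on 16 degrees of freedom, which gives power 81.2%. With 8 per arm it is 75.7%. So 9 per arm, 18 in total, and 18 / 0.9 = 20 recruited: the plan's figures reproduce.

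**2. Chance of a severity gap.** The documents give no severity distribution. Assume K of 20 patients are more severe and the arms are 10 v 10. The number of severe patients in one arm is hypergeometric: P(x) = C(K, x) × C(20-K, 10-x) / C(20, 10), with C(20, 10) = 184,756.
- K = 10: a tie (5 v 5) has 252² = 63,504 ways, probability 0.344. A 6 v 4 split either way has 2 × 210² = 88,200 ways, probability 0.477. A gap of 4 or more: 1 - 0.344 - 0.477 = 0.179.
- K = 8 (and, by symmetry, 12): a tie has 70 × 924 = 64,680 ways, 0.350. A gap of 2 has 2 × 56 × 792 = 88,704 ways, 0.480. A gap of 4 or more: 0.170.

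With severity as a continuous score, the standard error of the standardized difference is √(2/10) = 0.447. A difference above 0.5 SD then has probability 26%, and above 0.75 SD, 9%.

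**3. Size of the shift in PGI-I.** Shift = correlation × SD of PGI-I × standardized gap. For 7 v 3 with K = 10, the proportions differ by 0.4 and the SD of the severity indicator is 0.5, so the standardized gap is 0.4 / 0.5 = 0.8.
- Correlation 0.3 (assumed): 0.3 × 0.7 × 0.8 = 0.17 points.
- Correlation 0.5 (assumed): 0.5 × 0.7 × 0.8 = 0.28 points.

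A gap larger than 4 shifts it further, but a gap of 6 or more has probability of only about 2%.

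**4. Error rates.** Simulation of the exact Mann-Whitney test under no treatment difference (10 per arm, normal data, 60,000 runs per correlation):

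| Correlation (assumed) | Overall | Given imbalance > 0.5 SD | Given imbalance > 0.75 SD |
|---|---|---|---|
| 0.3 | 4.4% | 5.9% | 7.1% |
| 0.5 | 4.2% | 7.7% | 11.3% |

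**5. Precision available.** Adjustment multiplies the residual SD by √(1 - r²). At r = 0.3 it falls from 0.70 to 0.67, and t-test power at 9 per arm rises from 81% to about 85%. At r = 0.5 the SD falls to 0.61 and power rises to about 91%. These are approximations for a t-test that ignore the degree of freedom spent on the covariate. A rank-based analysis should gain in the same direction but not by exactly these amounts.

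**The case against.** The strongest reply is that simple randomization with an unadjusted rank test is a valid analysis of a 20-patient pilot, and that adjustment is only a matter of efficiency. The validity part stands: chance imbalance is already allowed for in the overall error rate. A reader might infer that the trial cannot tell a severity imbalance from a treatment effect, or that its test is biased. Step 4 does not support that.

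A reader might also infer that the protocol commits the very fault it blames for the earlier results. The documents do not go that far.
- Section 5 offers mismatch only as a possible explanation for some patients, after arguing for another cause: "It is therefore possible that poor outcome on subjective functional rating scale in both RCTs were related to weakness".
- The summary that closes Section 5 lists the limitations this trial is meant to address, and mismatch is not among them.
- The TRS threshold of 2 excludes the mild tremor that Section 5 contrasts with moderate-to-severe tremor.
- Section 5 describes harm at both ends of the range, so it gives neither a sign nor a size for the correlation.

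The chance of a gap of 2 or more is 65-66%, which looks alarming. But with 10 per arm and an even number of severe patients all gaps are even, so this figure means only that the split is not an exact tie.

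Finally, fixed strata such as TRS 2 versus 3 or more cannot be applied as the protocol stands, because the hand TRS is not defined. That is why the remedy begins with the analysis and with defining the score.

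**Conclusion.** The concern holds as a matter of precision and robustness, not of validity. The primary comparison ignores a baseline measure that is already collected and that the protocol itself thinks may matter. Under the assumed split of 8 to 12 severe patients in 20, a gap of at least 4 between arms has probability 17-18%. A 7 v 3 split moves the PGI-I difference by about 0.17-0.28 points at assumed correlations of 0.3-0.5. That is modest against the planned 1-point effect, and matters proportionally more if the true difference between two active arms is smaller.

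The severity split, the correlations and the 10 v 10 allocation are assumptions; only the SD of 0.7 and the 1-point effect come from the plan. If severity is unrelated to PGI-I, little is lost by leaving the plan as it is. The change is worth making because it costs almost nothing.

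**What to change.** 1. State in Section 7, Statistical analysis, that the week-6 PGI-I comparison is adjusted for baseline dominant-hand TRS by a rank-based method: rank ANCOVA on the baseline score, or a van Elteren test if the allocation list is stratified.
2. Name which of the six TRS items, or which sum, forms that score.
3. Optionally, if randomization has not begun, use small permuted blocks within two levels of that score, measured before the envelope is opened. Blocks of 2 hold the gap within a stratum to 1 patient and blocks of 4 hold it to 2, so a gap of 4 cannot occur.
4. Reconcile Section 5's criticism of fixed dosing with the fixed regimens in Section 7. Section 5 also calls both earlier trials fixed-dose, while Figure 1 shows a dose increase at week 4 in one of them; these passages need reconciling too. No dose is proposed here.

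**Cost:** a sentence or two in the analysis section, about one degree of freedom with 18 to 20 patients, and no change in sample size. If the list is stratified, it also needs two sets of envelopes, and incomplete blocks may leave the arms unequal by a patient or two (at worst 12 v 8 with blocks of 4).

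### QUEST is defined as a mean difference from baseline but computed as percent change, and no use is stated for the grip-strength baseline that the trial collects

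*Combined protocol and SAP*

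**What the plan says.** **QUEST.** Section 6, Secondary Outcome Measures, item 2 reads "Difference in the mean Quality of Life in Essential Tremor Questionnaire (QUEST) at Week 6 from baseline", compared between the two injection groups. Item 7 reads "Difference in the mean QUEST score at Week 12 from baseline", for the same comparison. Section 7, Statistical analysis, gives the only computation for this outcome: "we will compute percent change of TRS and QUEST for each follow-up visit as compared to the baseline". The test is named in one general sentence: "Given the small sample size, Mann-Whitney U test will be used for calculations".

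**Grip strength.** Items 4 and 9 of the same list read "Difference in grip strength post injection between the two groups at 6 weeks" and "Difference in grip strength post injection between the two groups at 12 weeks". Neither refers to baseline, although the QUEST items beside them do. Grip is measured before injection: section 7 says of the screening visit "In addition we will evaluate grip strength using dynamometer", and of the follow-up visits "At these times we will repeat all baseline measures". Figure 2 marks grip strength at all three visits. The Statistical analysis text does not mention grip.

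**The concern.** For QUEST, an analyst who follows section 6 and one who follows section 7 will report different quantities, and nothing in the plan says which prevails. A rank test on percent change does not estimate a difference in mean change.

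For grip, the plan pays for a baseline measurement and then states no use for it. Eligibility covers both sexes from age 18 upward, so stable strength differences between people can be expected. A follow-up-only comparison leaves them in the error term at 9 against 9. The hypothesis in section 6 is that flexor-only injection causes less weakness and therefore better global improvement. Grip is the one scheduled measure that puts a number on strength.

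**Working it through.** **1. The plan's own figure.** Section 7 gives a difference of 1 point, SD 0.7, alpha 0.05 and power 80%. The standardised effect is 1/0.7 = 1.43. A two-sided two-sample t-test then needs 8.76, so 9 per arm and 18 in total (power 81.2%); 18/0.9 = 20 recruited. The stated size reproduces. It rests on TRS and PGIS, so nothing below alters it.

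**2. Are the two QUEST quantities interchangeable?** Invented values, two patients per group:
- Group A goes 20 to 10 and 60 to 55. Mean change is (-10 - 5)/2 = -7.5 points; mean percent change is (-50.0 - 8.3)/2 = -29.2%.
- Group B goes 20 to 18 and 60 to 40. Mean change is (-2 - 20)/2 = -11.0 points; mean percent change is (-10.0 - 33.3)/2 = -21.7%.

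B does better in points and A does better in percent, so the two are not interchangeable.

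**3. How often would the verdict differ?** The documents give no QUEST mean, SD or correlation. Assumed: a 0-100 score, rounded and bounded, baseline mean 40, SD 15, baseline floor 5; 9 per arm; a 1 SD (15-point) effect; two-sided 0.05. With Mann-Whitney held fixed and only the scale changed (percent against absolute change), the verdicts differ in about 10, 14, 13 and 6% of simulated trials at baseline-to-follow-up correlations of 0.3, 0.5, 0.7 and 0.85. A second set of runs gave 11, 12, 14 and 7%, so gaps of a point or two are simulation noise. With no true effect the verdicts differ in about 2%.

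**4. Grip precision at 9 v 9, in SD units of follow-up grip.**
- Follow-up only: SE = sqrt(2/9) = 0.471; half-width = 2.120 (t, 16 df) x 0.471 = 1.00.
- Baseline-adjusted: the variance is multiplied by (1 - r²)(1 + 1/14), where 1/14 is the expected cost of estimating the slope; t is 2.131 (15 df).

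| Assumed r | Variance ratio | SE | 95% CI half-width |
|---|---|---|---|
| 0.3 | 0.975 | 0.465 | 0.99 |
| 0.5 | 0.804 | 0.423 | 0.90 |
| 0.7 | 0.546 | 0.348 | 0.74 |
| 0.85 | 0.297 | 0.257 | 0.55 |

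The half-widths are equal at r = 0.28; below that, adjustment gains nothing. These figures need no assumption about the size of the grip effect.

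**The case against.** *The QUEST wording may be loose rather than contradictory.* Section 6 says the comparison is from baseline and does not say score points. Section 7 could be read as stating how that change is computed. It also says only that percent change will be computed; that percent change is what the Mann-Whitney test compares is the likely reading, but an inference. This stands in part: one clarifying sentence would end the ambiguity. Until it is written, a difference in means and a rank test on percentages remain different quantities.

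*Different estimates need not mean different conclusions.* True. If all nine patients in each arm fall 8 points, with baselines of 15-55 and 25-65 in steps of 5, the difference in mean change is 0 while mean percent change is -27.0% against -19.5%. Mann-Whitney on those percentages gives p = 0.17, so no verdict changes.

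*Follow-up-only grip is one reading.* The wording does not exclude use of the baseline, and the general Mann-Whitney sentence can be taken to cover grip. This stands too. The gap is that no grip analysis is named and no use of its baseline is stated.

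*A reader might infer that the grip comparison is biased, or that percent change costs QUEST power.* Neither is supported. Randomisation protects the follow-up-only comparison, so the cost is precision alone. On the same assumed QUEST inputs, percent change has about the same power as a rank test on baseline-adjusted values once the correlation reaches about 0.7 (70 v 70%, then 92 v 91%).

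**Conclusion.** The point holds for four of the nine secondary outcomes (items 2, 4, 7 and 9). QUEST has two non-equivalent specifications. Under the stated assumptions, the choice of scale alone changes the significance verdict in roughly 6 to 14% of trials of this size when there is a 1 SD effect. Grip has a collected baseline with no stated use. Adjusting for it would shorten the interval by about 1% at r = 0.3, 10% at 0.5, 26% at 0.7 and 45% at 0.85.

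All of these are ranges: the documents give no correlation or SD for either measure, nor any expected grip effect. The 1.43 SD effect behind the sample size belongs to TRS and PGIS and should not be carried over to grip, particularly as both arms receive the same flexor doses.

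A reader might infer that the main result or the trial size is in doubt. It is not: the primary PGI-I and the 18/20 sample size do not depend on these analyses. Which TRS score is analysed is a separate clarification. This should be corrected before analysis, but it is not a flaw in the design.

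**What to change.** In section 6 (items 2, 4, 7 and 9) and in section 7, Statistical analysis, define QUEST and dominant-hand grip at weeks 6 and 12 as the baseline-adjusted between-group difference. Estimate it by ANCOVA, regressing the follow-up value on arm and the patient's own baseline, and report it with its 95% CI. Take the p-value from the same model, by permutation if preferred for so small a sample, and state that choice in advance. Keep percent change and the unadjusted Mann-Whitney test as descriptive or sensitivity analyses.

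Keeping the rank test by applying it to baseline residuals, beside an ANCOVA interval, would be a poorer repair. In simulation the two disagree on significance in about 5 to 10% of trials, and the rank test has less power (44, 54, 70 and 92% against 51, 60, 77 and 95% at the four correlations).

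The cost is wording and analysis code only; both baselines are already in Figure 2, so no visit, measurement or patient is added. The model spends one degree of freedom and assumes a roughly linear relation to baseline. It gains almost nothing for grip at a correlation of about 0.3 or below. If the sponsor prefers another single QUEST variable, stating it identically in both sections would also remove the mismatch.
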